4.4 End of Study Definition

A participant is considered to have completed the study if he or she has completed all phases of the study including the last visit or the last scheduled procedure shown in the Schedule of Activities (SoA), Section 1.3.

The end of the study is defined as completion of the last visit or procedure shown in the SoA in the trial globally.

5. STUDY POPULATION

5.1 Inclusion Criteria

Study candidates must meet all of the following inclusion criteria to be eligible for participation in this study:

- a. Adults \geq 18 years
- b. Life expectancy of 6 months or more as determined by the investigator
- c. HCC confirmed by Liver Reporting & Data System (LIRADS) on MRI or CT
- d. Must have measurable disease, defined as at least one lesion that can be accurately measured in at least one dimension (longest diameter to be recorded for non-nodal lesions and short axis for nodal lesions) as \geq 20 mm (\geq 2 cm) with CT scan, MRI, or calipers by clinical exam. See Section 12 (Measurement of Effect) for the evaluation of measurable disease.
- e. \leq 3 lesions
- f. Longest dimension of the largest lesion \leq 7cm
- g. Single lobe disease
- h. No significant extrahepatic metastatic disease
- i. Barcelona Clinic Liver Cancer Stage A, B or C
- j. ECOG $<$ 2 (Appendix A)
- k. Lesion(s) $<$ 50% of liver volume
- l. Bilirubin \leq 2 mg/dL
- m. Albumin \geq 3 g/dL
- n. PT/INR $<$ 2
- o. AST/ALT \leq 3 institutional upper limit of normal (ULN)
- p. Platelet count $>$ 50,000/mcL
- q. Lung shunt fraction of $<$ 20% by planar MAA if dose modification results in inadequate dose delivered to the tumor(s)
- r. Patients with a prior or concurrent malignancy whose natural history or treatment does not have the potential to interfere with the safety or efficacy assessment of the investigational regimen are eligible for this trial.
- s. Completion of all previous therapy (including surgery, radiotherapy, chemotherapy, immunotherapy, or investigational therapy) for the treatment of cancer \geq 12 week before the start of study therapy.
- t. Willingness and ability of the subject to comply with scheduled visits, drug administration plan, protocol-specified laboratory tests, other study procedures, and study restrictions.
- u. Evidence of a personally signed informed consent indicating that the subject is aware of the neoplastic nature of the disease and has been informed of the procedures to be followed, the experimental nature of the therapy, alternatives, potential risks and discomforts, potential benefits, and other pertinent aspects of study participation.
- v. The effects of *Y90 microspheres* on the developing human fetus are unknown. For this reason female of child-bearing potential (FCBP) must have a negative serum or urine pregnancy test prior to starting therapy.

w. FCBP and men must agree to use adequate contraception (hormonal or barrier method of birth control; abstinence) prior to study entry and for the duration of study participation. Should a woman become pregnant or suspect she is pregnant while she or her partner is participating in this study, she should inform her treating physician immediately. Men treated or enrolled on this protocol must also agree to use adequate contraception prior to the study, for the duration of study participation, and 4 months after completion of *[IND Agent]* administration. A female of childbearing potential (FCBP) is a sexually mature woman who: 1) has not undergone a hysterectomy or bilateral oophorectomy; or 2) has not been naturally postmenopausal for at least 24 consecutive months (i.e., has had menses at any time in the preceding 24 consecutive months.

5.2 Exclusion Criteria

An individual who does not meet all the inclusion criteria in section 5.1.

6. REGISTRATION PROCEDURES

Patients will be registered after meeting all entry requirements and signing of the informed consent document.

6.1 Local Winship Procedures

Study personnel will notify Winship Central Subject Registration (WCSR) by email at [REDACTED] once subject has been consented for a trial.

Email notification must be done within 24 hours after consent has been obtained and it will include scanned copies of:

- Signed patient consent form
- HIPAA authorization form
- Emory Research Management System (ERMS) Enrollment Fax Cover

The WCSR will enter the subject into the OnCore Research Management System, which is the system of record for Winship Cancer Institute Clinical Trials.

6.2 Enrollment / Randomization and Blinding

Enrolling a subject requires careful screening and determination of eligibility.

Eligible patients will be enrolled on study centrally at Winship Cancer Institute by the Study Coordinator.

When all required test results are available, complete the eligibility checklist and provide the checklist and the supporting documentation to the IRB approved investigator for review and sign-off. Once the investigator (sub-investigator, Co-Investigator) has signed the eligibility checklist, randomization and or enrollment may proceed. Oncore and ERMS must be updated to reflect eligibility and on treatment status.

Following enrollment, patients should begin protocol treatment within 7 business days. Issues that would cause treatment delays should be discussed with the Principal Investigator.

7. STUDY INTERVENTION

7.1 Agent Administration (or Study Intervention Administration)

7.1.1 Study Intervention Description

The low-dose Y90 (15 mCi), will remain the same for all the patients. As explained in section 4.3, this dose ensures adequate imaging on both SPECT and PET without the risk of developing radiation induced pneumonitis in the setting of high LSF.

The therapeutic dose of Y90 will be calculated using the partition model detailed below based MAA biodistribution in the tumor, non-tumoral liver and the lungs.

7.1.2 Dosing and Administration

Treatment will be administered on an *outpatient* basis. Reported adverse events and potential risks are described in Section 7. Appropriate dose modifications are described in Section 8. No investigational or commercial agents or therapies other than those described below may be administered with the intent to treat the patient's malignancy.

No dose escalation or dose expansion is planned in this procedure.

The treatment Y90 dose will be calculated using the partition model as detailed below:

The required therapeutic Y90 dose will be calculated using MAA SPECT, Y90 SPECT and Y90 PET. **Although all 3 sets of calculations will be made prospectively, the activity calculation based on MAA SPECT (the standard of care) will be used for actual treatment planning.** The activities calculated using Y90 SPECT and PET will be used for post-hoc analysis. Partition model to achieve cytotoxic Target Tumor Dose of >100 Gy will be utilized using the following formulas[7]:

- 1) **Desired Tumor Activity (GBq) = (100 Gy X Tumor Mass (Kg)) / 50**
- 2) **Targeted Normal Liver Activity (GBq) = Desired Tumor Activity (GBq) / TNR**
- 3) **Targeted Liver Lobe Activity (GBq) = (Targeted Normal Liver Activity + Desired Tumor Activity) (GBq)**
- 4) **Targeted Liver Lobe Dose (Gy) = Targeted Liver Dose Activity (GBq) X 50 / Liver mass (Kg)**

The liver and tumor mass will be determined using the volumes calculated by MIM software and assuming density of 1.03 g/cm³ [39]. It will be ensured that targeted liver dose remains below 50 Gy which has been shown to be safe with no sequela of radiation induced liver disease while ensuring the target tumor dose >100 Gy[7, 26].

5) Y90 Activity for administration (GBq) = Targeted Liver Lobe Activity (GBq) X (1+LSF)

Lung dose after therapeutic Y90 RE will be calculated using the following formula:

6) Lung Dose (Gy) = Y90 Activity to be Administered (GBq) X LSF X 50 / Mass of Lungs (Kg)

Lung Dose <30Gy will be ensured by reducing administered activity if needed (lung mass assumed at 1 Kg)[8].

The MAA, low-dose and therapeutic dose Y90 microspheres will be administered intra-arterially using the following technique:

Radial or femoral arterial access will be obtained. A 5 Fr catheter will be used to select superior mesenteric artery and celiac trunk. A 2.8 Fr microcatheter will be advanced to the right or left hepatic artery branch supplying the targeted HCC lesion(s). From this location, detailed evaluation of hepatic arterial vasculature using conventional angiography and 3D cone beam CT (CBCT) will be performed to ensure complete perfusion of the targeted tumor(s) and absence of visible non-target embolization. If a potential non-target vessel (i.e. gastroduodenal or right gastric artery) is observed, the vessel will be embolized using coils or plugs during the first mapping study using MAA. From the catheter location where CBCT will be performed to ensure complete perfusion of the tumor and lack of non-target supply. Then MAA, low-dose or therapeutic dose Y90 will be administered.

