4. STUDY DESIGN

4.1 Overall Design

This study is a single arm phase II prospective clinical trial in which patients with HCC who are deemed suitable for Y90 radioembolization will be recruited. Patients will undergo standard of care mapping study with ^{99}Tc -MAA to plan for Y90 radioembolization therapy. The additional, non-standard of care, intervention will be to do a second mapping study using low-dose Y90 (15 mCi) before the therapeutic Y90 radioembolization.

The distribution of MAA in terms of lung shunt fraction (LSF) and tumor to normal liver activity ration (TNR) will be compared to that of low-dose Y90. The treatment planning will be performed using standard of care MAA biodistribution using partition dosimetry model.

After administration of therapeutic Y90 dose, the actual dose delivered to tumor, non-tumoral liver (NTL) and lungs will be compared to the dose predicted by MAA and low-dose Y90.

The patients will be followed-up clinically and with imaging at 1, 3 and 6 months to determine tumor response, potential treatment related toxicity and to determine TDRT.

Hypothesis: Low dose Y90 microspheres as the treatment planning radiotracer will allow more accurate prediction of therapeutic Y90 liver biodistribution, which will enable us to perform prospective personalized dosimetry for every individual patient.

The results of this study will determine the safety and efficacy of using low dose Y90 as a direct surrogate for treatment planning to ensure delivering cytotoxic Y90 dose to the targeted tumor(s), while concomitantly minimizing liver and lung toxicity with more accurate prediction of therapeutic Y90 biodistribution. **Our long-term objective is to increase the likelihood of objective tumor response, prolonged progression-free survival (PFS) and overall survival (OS) in patients with HCC treated with Y90 RE.**

The study is a single-arm in study in which each patient will undergo two sets of mapping procedure before the actual Y90 therapy. One with standard of care ^{99}Tc -MAA and one with low-dose (15 mCi) Y90 microspheres. **Therefore, the additional intervention in the study is the second mapping procedure with low-dose Y90 microspheres.** Each patient will be used as their internal control to minimize selection biases. **Additional to standard of care Y90 SPECT/CT after therapy, the patient will undergo one PET/CT after low-dose Y90 and one PET/CT after Y90 therapy.**

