v. **Y90 Activity for administration (GBq) = Targeted Liver Lobe Activity (GBq) X (1+LSF)**

Lung dose after therapeutic Y90 RE will be calculated using the following formula:

vi. **Lung Dose (Gy) = Y90 Activity to be Administered (GBq) X LSF X 50 / Mass of Lungs (Kg)**

Lung Dose <30Gy will be ensured by reducing administered activity if needed (lung mass assumed at 1 Kg)[8].

H. 3rd Angiography and Administration of Y90 Therapy Dose (Wednesday/Thursday)

The actual prescribed Y90 activity as calculated above using MAA SPECT (**the current standard of care**) will be administered on Wednesday or Thursday of the same week after the shunt study. The desired activity will be drawn from the remainder of activity in the 5-day flex resin microsphere vial. It will be administered by [name] using the same catheter techniques described above. **After the procedure, patient's femoral sheath will be removed and hemostasis will be achieved with manual compression or closure device. If procedure performed via radial access, which is more commonly performed currently at Emory, the radial sheath will stay in and removed according to IR protocol after Y90 SPECT/CT.** The patient will be then transported to nuclear medicine department of Y90 SPECT/CT.

I. Therapeutic-dose Y90 Planar and SPECT/CT (Wednesday/Thursday)

Using the same technique described above (section E), planar and SPECT/CT will be performed using medium energy filter. The patient will then be discharged from IR after removal of the radial sheath according to our standard protocol.

J. Therapeutic-dose Y90 PET/CT of chest and abdomen (Wednesday/Thursday)

The patient will then undergo time of flight Y90 PET/CT with one or two bed positions depending on the patient's size. This will also occur on the same day and at the same location as the remainder of mapping day either at EUH or EUHM.

Below is the conservative estimated timeline of Mapping/shunt studies performed on Wednesday or Thursday:

11:00 AM-12:30 PM: 3rd angiographic study to deliver therapeutic dose of Y90.

1:00 PM-2:00 PM: Y90 Bremsstrahlung SPECT/CT (After the procedure, patient's femoral sheath will be removed and hemostasis will be achieved with manual compression or closure device. If procedure performed via radial access, which is more commonly performed currently at Emory, the radial sheath will stay in and removed according to IR protocol after Y90 SPECT/CT.)

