3:00 PM-3:30 PM: Removal of the radial sheath at IR post procedural area and discharge.

4:30-5:30 PM: Y90 PET/CT at Cardiac PET center on the 4th floor of EUHM.

Patient is free to go home after this.

K. Y90 Therapy Tumor, Liver, and Lung Dose Calculation (Friday)

Utilizing the MIM software, post Y90 therapy PET/CT data and partition method described above, the mean actual dose delivered to the tumor, normal liver, and lung will be calculated by Drs. [name] and [name]. The software will generate ROIs from the inside to the periphery of the tumor based on Y90 delivery, and Dose Volume Histograms (DVH) plotting the delivered dose as a function of liver volume. Using DVH, % of tumor volume receiving >100Gy and dose range to the tumor will be also calculated.

L. Follow-up phone call [REDACTED] or study nurse (1-week post therapy)

Patient will be followed by phone to ensure they are doing well, and they will be screened for any symptoms related to adverse events. If any concerning symptoms is reported, they will be brought to IR clinic for further evaluation.

M. 1-Month clinical and Imaging Follow-up

- Multiphase liver mass protocol MRI or CT will be obtained
- Brief medical history
- Symptom-directed physical exam
- ECOG Performance Status
- Vitals signs
- Review of prior/concomitant medications
- Clinical laboratory tests for:
 - Hematology
 - CMP

N. 3-Month clinical and Imaging Follow-up

- Multiphase liver mass protocol MRI or CT will be obtained
- Brief medical history
- Symptom-directed physical exam
- ECOG Performance Status
- Vitals signs
- Review of prior/concomitant medications
- Clinical laboratory tests for:
 - Hematology
 - CMP

O. 6-Month clinical and Imaging Follow-up

- Multiphase liver mass protocol MRI or CT will be obtained
- Brief medical history
- Symptom-directed physical exam
- ECOG Performance Status

- Vitals signs
- Review of prior/concomitant medications
- Clinical laboratory tests for:
 - Hematology
 - CMP

End of Treatment

End of treatment is defined as the last planned Y90 therapy within the 6-month dosing period. For subjects who discontinue drug treatment prior to 6 months, end of treatment is considered the last visit where the decision is made to discontinue treatment. All required procedures may be completed within \pm 7 days of the end of treatment visit. Repeat disease assessment is not required if performed within 28 days prior to the end of treatment visit.

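### The primary objective asks which tracer better predicts delivered dose, but the plan defines no tracer-specific predicted tumor or normal-liver dose and tests neither tracer against delivered dose

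*Combined protocol and SAP*

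**What the plan says.** The synopsis and Section 3 make the primary objective a comparison of low-dose Y90 and MAA as predictors of the dose that therapy delivers to tumor, liver and lung. Section 4.1 says that "the actual dose delivered to tumor, non-tumoral liver (NTL) and lungs will be compared to the dose predicted by MAA and low-dose Y90".

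Section 7.1.2, repeated in 8.1 G and continued after it, gives six formulas:

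- The first is "Desired Tumor Activity (GBq) = (100 Gy X Tumor Mass (Kg)) / 50".
- The second is "Targeted Normal Liver Activity (GBq) = Desired Tumor Activity (GBq) / TNR".
- The third adds the two activities.
- The fourth converts that sum to a dose over the liver mass.
- The fifth multiplies the sum by one plus LSF to get the activity to give.
- The sixth gives lung dose from the activity to be administered, LSF and lung mass.

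The same section says "The required therapeutic Y90 dose will be calculated using MAA SPECT, Y90 SPECT and Y90 PET". Only the MAA result governs treatment. The activities from the two low-dose Y90 scans go to post-hoc analysis.

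Section 8.1 K obtains delivered dose from "post Y90 therapy PET/CT data and partition method described above, the mean actual dose delivered to the tumor", and adds dose-volume histograms from the software.

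In Section 10.1 both hypotheses set Y90 against MAA, one on LSF and one on TNR. Section 10.3 tests them with a paired t-test. Sections 10.4 and 10.5.4 relate tumor dose to response, or again compare MAA with Y90. Nowhere in Section 10 is a predicted dose compared with a delivered one.

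**The concern.** There are two gaps, and they compound.

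First, the predicted dose is not defined. The first formula takes 100 Gy and tumor mass as inputs and contains nothing from any scan. TNR and LSF enter later and change only the activities. The fourth formula does return a dose, but it pools tumor with normal liver, so it is neither a tumor nor an NTL dose. The promised comparison therefore has no stated predicted value for two of its three compartments.

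Second, the stated analysis does not address the objective. A paired test of LSF and TNR shows whether the two tracers differ. It cannot show which lies closer to what therapy delivered. Left open, the definition of predicted dose and the error measure would be chosen after the data are in, and one plausible choice removes almost all information about the tracers from the tumor comparison.

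**Working it through.** **The plan's own figure.** Section 4.3 states 27.8 Gy to the lungs from 15 mCi at an LSF of 100%. The sixth formula gives 15 × 0.037 GBq × 1.00 × 50 / 1 kg = 27.75 Gy, so it reproduces.

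**Inputs (Section 10.2).** LSF is 11.66% for MAA and half of that, 5.83%, for low-dose Y90. TNR is 5.4 for MAA and 5.4/0.7 = 7.71 for low-dose Y90.

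**Activity per unit of tumor activity** (second, third and fifth formulas), (1 + 1/TNR) × (1 + LSF):

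- MAA: (1 + 1/5.4) × 1.1166 = 1.3234
- Low-dose Y90: (1 + 1/7.714) × 1.0583 = 1.1955

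**Forward tumor dose.** Rearranging the formulas gives tumor dose = A × (1 − LSF) × TNR/(1 + TNR) × 50 / tumor mass. The protocol does not print this. Tumor mass cancels once A comes from the 100 Gy target.

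*Each tracer at its own planned activity.* The expression reduces to 100 × (1 + LSF)(1 − LSF) = 100 × (1 − LSF²):

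- MAA: 100 × (1 − 0.1166²) = 98.6 Gy
- Low-dose Y90: 100 × (1 − 0.0583²) = 99.7 Gy

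TNR has dropped out, so these values say almost nothing about the tracer.

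*Both tracers at the activity given (the MAA plan).*

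- MAA: 98.6 Gy
- Low-dose Y90: 100 × 1.3234 × 0.9417 × 7.714/8.714 = 110.3 Gy

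The difference is 11.7 Gy, a ratio of 1.12. Over assumed ranges (MAA TNR 3.3 to 7.5, Y90-to-MAA TNR ratio 1 to 2, MAA LSF 5% to 20% and halved for Y90), the MAA prediction runs from 96 to 99.8 Gy and the low-dose Y90 prediction from 102 to 122 Gy.

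**Why the LSF and TNR tests cannot decide.** On a log scale the midpoint of the two predictions is √(98.64 × 110.32) = 104.3 Gy. A delivered dose below that makes MAA the better predictor; one above it makes low-dose Y90 the better. The Section 10.3 tests give the same result in both cases, because delivered dose does not enter them.

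**Definition of TNR.** The second formula divides tumor activity by TNR to get normal-liver activity, which treats TNR as a ratio of total activities. In the phantom (Section 2.2.2) the spheres held 2.9 mCi and the liver compartment 10.9 mCi, a total ratio of 0.27, yet the true TNR is given as 10. That figure cannot be a total-activity ratio.

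To show how much this matters, assume a 0.1 kg tumor in a 0.8 kg lobe (0.7 kg NTL), keep the MAA-planned activity of 0.2647 GBq, and read TNR as a concentration ratio:

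- MAA: tumor share 0.54/(0.54 + 0.70) = 0.435, and 0.2647 × 0.8834 × 0.435 × 50/0.1 = about 51 Gy
- Low-dose Y90: tumor share 0.771/(0.771 + 0.70) = 0.524, and 0.2647 × 0.9417 × 0.524 × 50/0.1 = about 65 Gy

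The same MAA scan thus yields 98.6 or about 51 Gy depending on a definition that the plan leaves inconsistent. Inverting the printed formulas, as the reference in 8.1 K to the partition method suggests, would carry that ambiguity into delivered dose as well.

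**The case against.** The authors can fairly say that the forward calculation is within reach. Section 2.1 says that the partition model gives separate doses for tumor and NTL. Section 8.1 E, a low-dose Y90 step, says that compartment proportions plus a known administered activity are enough to compute dose. Delivered dose is measured from PET/CT with software histograms. Each tracer's LSF and TNR are the declared endpoints, so the inputs will exist. All of that stands, and it shows that the fix agrees with the authors' intent. It does not put a predicted dose or an error measure into the formulas, 8.1 K or Section 10.

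A reader might infer more than the documents support:

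- *That the formulas go only from target to activity.* The fourth and sixth formulas and the 27.8 Gy example run from activity to dose.
- *That the predicted tumor dose is 100 Gy for every tracer and patient, so the tracer difference is exactly zero and a correlation with delivered dose is undefined.* No section defines the prediction as the target. The plan specifies no correlation of predicted with delivered dose; Section 10.3 mentions Pearson coefficients only in general terms. Dose limits also change some plans. For example, three 7 cm lesions (0.555 kg) at TNR 5.4 give 2 × 0.555 × 1.185 × 50 / 1 kg = 65.8 Gy for an assumed 1 kg lobe, above the 50 Gy limit.
- *That the low-dose lung prediction is biased because it uses an activity that was never given.* The sixth formula reads "Lung Dose (Gy) = Y90 Activity to be Administered (GBq) X LSF X 50 / Mass of Lungs (Kg"), and the administered activity is the MAA-based one. On that natural reading there is no bias.

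**Conclusion.** The concern holds as a mismatch between objective and analysis. The plan sets out to find which tracer better predicts delivered dose, defines no tracer-specific tumor or NTL prediction at the administered activity, and specifies no comparison of either tracer with delivered dose. This is more than missing detail, because the Section 10.3 analysis as written cannot answer the primary objective.

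At the planning means, the unstated choice moves the contrast between tracers from 98.6 and 99.7 Gy (own plans) to 98.6 and 110.3 Gy (common activity). These figures assume that no dose limit binds and that TNR is a total-activity ratio. The figures of about 51 and 65 Gy under a concentration ratio also rest on assumed masses.

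The LSF and TNR tests, the sample size and treatment planning do not depend on this point.

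**What to change.** Add an analysis-only calculation to 8.1 K and 10.3:

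1. For each planning scan (MAA SPECT, low-dose Y90 SPECT, low-dose Y90 PET), predicted dose = 50 × activity actually administered × that scan's share of activity in the compartment / compartment mass, for tumor, NTL and lung.
2. Compute delivered dose with the same equation from the post-therapy PET/CT.
3. Compare the size of the prediction error between MAA and low-dose Y90 within patients by a paired analysis. Use the log of predicted over delivered for tumor and NTL. Use the absolute difference for lung, where values may be near zero and a ratio would be unstable. Name in advance which low-dose scan carries the main comparison.
4. State whether TNR is a concentration ratio or a total-activity ratio, and reconcile the second formula with the phantom's TNR of 10. Working from compartment shares keeps the dose comparison itself independent of that choice.

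The cost is a few lines of text and one extra calculation per scan. No new scans or patients are needed.
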